We intend to perform a non-inferiority two-arm randomized controlled trial to evaluate the safety and feasibility of prophylactic salpingectomy at the time of a cesarean delivery as an initiative to avoid a missed opportunity in the primary prevention of ovarian cancer. Once enrolled and consented, women will be randomized using a stratified block randomization algorithm according to number of prior cesarean deliveries and BMI to either salpingectomy or bilateral tubal ligation. The data collection will include preoperative CBC, time of procedure, postoperative CBC at 24 hours, standard patient demographics, procedural complications, estimated blood loss, return to the OR, length of stay, pain scores and postoperative complications including readmission within 6 weeks.

Interventions and Duration

In the control arm, subjects will have sterilization performed via the Parkland or Pomeroy method of bilateral tubal ligation based on provider preference. In the study arm, a salpingectomy will be performed using a combination of suture ligation and cautery. The enrollment period will occur over two years and follow up will extend 6 weeks from surgery.

Sample Size and Population

The study population will included pregnant woman greater than 21 years old that have an indication for cesarean delivery and proper consent for permanent sterilization. The stratified block randomization will be according to number of prior cesarean deliveries (primary versus repeat cesarean delivery). The primary outcome is mean drop in hemoglobin. Assuming that a difference of 0.5 in the drop in hemoglobin between study arms would be considered as equivalent and assuming a common standard deviation of 1.1, the study will have 80% power to test for non-inferiority with 60 patients in each arm (120 totals). This calculation is based on a two-group 0.05 1-sided t-test of equivalent in means.

1 STUDY OBJECTIVES

1.1 Primary Objective

Identify the mean difference in pre and postoperative hemoglobin for patients undergoing salpingectomy for sterilization vs patients undergoing standard bilateral tubal ligation (BTL) via mid-segment resection of the fallopian tube at the time of cesarean delivery.

1.2 Secondary Objectives

1. Identify the time for performance of a salpingectomy vs a standard BTL at the time of cesarean delivery
2. Identify rates of procedural complications for patients undergoing salpingectomy vs a BTL at the time of cesarean delivery
3. Identify rates of readmission/take back to OR, length of stay, estimated blood loss (EBL) and pain scores in patients undergoing a standard BTL vs a salpingectomy at the time of cesarean delivery.

2 BACKGROUND AND RATIONALE

2.1 Background on Condition, Disease, or Other Primary Study Focus

Ovarian cancer has the highest mortality of all gynecologic malignancies and is the fifth leading cause of cancer death women (1). Approximately 95% of ovarian cancer arises from the epithelial cells, of which serous carcinoma is the most common subtype. Serous ovarian carcinoma can arise from the ovary itself or arise from the fallopian tube. Increasing evidence suggests the origin of extra uterine pelvic serous carcinomas arises in the fallopian tubes, especially those that are high grade and associated with poor prognosis. There are no accepted screening methods for such cancers, and symptoms of disease are vague and non-specific, which contribute to higher stage and grade at the time of diagnosis. In view of this the American College of Obstetrics and Gynecology in its Committee Opinion (ACOG) in 2015 recommended US clinicians to counsel patients about prophylactic salpingectomy as an effective method of sterilization, which may offer us a way to prevent ovarian carcinogenesis(1).

Permanent sterilization with tubal ligation as a form of contraception is the most common method used worldwide. The National Health Statistics Report of 2015 states that 9.4 million (approximately 15%) women between ages 15-44 are currently using sterilization as a method of birth control, making it the second most common contraceptive method used following contraceptive pills(2). There are several types of tubal ligation: the postpartum tubal ligation (performed within the first six days after delivery), laparoscopic (or interval) method, and hysteroscopic method. In the United States, over 50% of all sterilization procedures are performed in the postpartum period.

ACOG considers postpartum sterilization as one of the safest and most effective methods of contraception, with 10 % of women undergoing hospital deliveries opting for it (3). ACOG states that when sterilization is performed concurrently with a cesarean delivery

in comparison to postpartum sterilization, any higher risks are those attributed to the cesarean delivery itself and not to the sterilization(4). Pomeroy, modified Pomeroy, and the Parkland methods of mid segment excision are the most common techniques used for sterilization during a cesarean delivery (4). With the recent ACOG committee opinion on offering prophylactic salpingectomy at the time of sterilization counseling, numerous physicians have begun performing salpingectomy during interval sterilization but there are mixed opinions about its use for sterilization postpartum and prophylactically during a cesarean delivery especially with respect to the its safety. Not performing a prophylactic salpingectomy at the time of a cesarean delivery might present itself as a missed opportunity for prevention of ovarian cancer.

2.2 Study Rationale

Opportunistic removal of bilateral fallopian tubes as a preventive procedure against development of ovarian, fallopian tube, and primary peritoneal cancers has been performed increasingly over the last five years. Surgical removal of the fallopian tubes is done during pelvic surgery for another indication, typically hysterectomy. It has also been performed in place of a tubal ligation in women desiring permanent sterilization. The procedure is offered to women who are deemed to be at average risk for ovarian cancer. Currently, women in British Columbia who undergo salpingectomies at the time of tubal sterilization are being followed as a cohort to determine the incidence of cancer in this group.(5) It is estimated that it will take fifteen years to find the definitive answer.

McAlpine et al. (2014) in a retrospective cohort study of 43,931 women in British Columbia showed that salpingectomy at the time of a hysterectomy and interval sterilization did not increase operative/perioperative risks and that it was safe and feasible(5). Recent studies have shown no increased risk in surgical morbidity when performing bilateral salpingectomies in an opportunistic manner as a replacement for sterilization procedures (6). There has been shown to be a slightly higher operating room time (approximately 10 minutes). There are no data from which to comment on ovarian reserve function after the procedure, and no data yet regarding the incidence of gynecologic malignancies in this cohort. Several practices are already offering opportunistic salpingectomies to patients who desire permanent sterilization and are being performed instead of bilateral tubal ligations.

To our knowledge to date there are no published studies that have looked at the use of prophylactic salpingectomy during a cesarean delivery. Our hypothesis is that performing bilateral salpingectomy in patients who desire permanent sterilization at the time of cesarean delivery will have equivalent surgical risk of blood loss, as measured by the drop in hemoglobin, compared to BTL at the time of cesarean delivery. The majority of women who develop ovarian cancer do not have a family history and therefore not undergoing specific surveillance. Women who are undergoing the surgical risk of a cesarean delivery and bilateral tubal ligation may gain long term benefit from a salpingectomy without an increase in their surgical risk.

A better understanding of the safety of prophylactic salpingectomy at the time of a

cesarean delivery will help us with counseling patients about the risks versus ovarian cancer preventions benefits of the procedure. It has the potential of changing and standardizing practice across the nation. We plan to register our trial in clinicaltrials.gov. We also plan to publish our study findings in a reputable journal.

3 STUDY DESIGN

We intended to perform a non-inferiority two-arm randomized controlled trial to look into the safety and feasibility of prophylactic salpingectomy at the time of a cesarean delivery, versus bilateral tubal ligation (BTL), via Parkland, or modified Pomeroy method as an initiative to avoid a missed opportunity in the primary prevention of ovarian cancer. Our primary outcome is to compare mean difference in pre and postoperative hemoglobin. The secondary outcomes are to compare total time completion, complications rates, readmission rates, reoperations rates, and length of hospital stay.

The study population will included pregnant woman greater than 21 years old that have an indication for cesarean delivery and proper consent for permanent sterilization. In the control arm (BTL), subjects will have sterilization performed via the Parkland or Pomeroy method based on provider preference. In the study arm, a salpingectomy will be performed and the entire fallopian tube will be excised using a combination of suture ligation and cautery.

The enrollment period will occur over two years and follow up will extend 6 weeks from surgery. The patients will primarily be recruited and enrolled in the clinic during their antepartum visits. However, patients who present to labor and delivery and are found to require a Cesarean delivery may be consented on admission. If an emergency cesarean delivery (alpha or beta) is required and the patient has not been consented earlier, they will not be a candidate for enrollment. The surgery will take place in the operating room on labor and delivery. Once enrolled and consented, women will be randomized using a stratified block randomization algorithm prepared by the study statistician to either salpingectomy or standard BTL stratified according to number of prior cesarean deliveries (first versus repeat) and BMI (BMI < 35, BMI > 35).

Prior to the procedure a preoperative CBC will be performed. Patients will undergo the cesarean delivery and once stable from that procedure, will progress to either salpingectomy or bilateral tubal ligation per the randomization. Time from start to conclusion of the sterilization procedure will be logged to obtain operative time. Post procedure, the type of sterilization procedure will be disclosed to the patient. A postoperative CBC will be performed the next day at least 24 hours but no later than 48 hours after the conclusion of the procedure. In addition to standard patient demographics (age, race, parity, body mass index, etc), data collection will include procedural complications, return to the OR, length of stay, and postoperative complications including readmission within 6 weeks.

The primary outcome is mean drop in hemoglobin. Previous studies have reported a mean (SD) drop in hemoglobin of 1.32 (0.94) g/dl following a repeat cesarean delivery

and 1.40 (1.2) following a first cesarean delivery (7). Based on our experience in 2015, we anticipate that over 75% of our cases will be repeat cesarean deliveries. Assuming that a difference of 0.5 in the drop in hemoglobin between study arms would be considered as equivalent and assuming a common standard deviation of 1.1, the study will have 80% power to test for non-inferiority with 60 patients in each arm (120 totals). This calculation is based on a two-group 0.05 1-sided t-test of equivalent in means.

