5.2 Handling of Study Interventions

There are no drugs or lifestyle/behavioral interventions in the study.

The intervention being investigated is the safety of salpingectomy as a form of sterilization vs BTL at the time of Cesarean delivery. Patients meeting enrollment criteria are those who desire permanent sterilization, are correctly consented, and are planning a repeat cesarean delivery. They will be blinded to the operative intervention at the time of

enrollment and randomization; after the surgery, it will be disclosed to them the procedure they had performed.

To investigate differences in mean hemoglobin, preoperative hemoglobin and postoperative hemoglobin will be obtained for all study participants.

To investigate the differences in operative time for the different surgical procedures being studied, all surgeries will be timed beginning at the initiation of the sterilization procedure being performed (i.e., once the cesarean delivery has been completed, and just prior to starting either the tubal ligation or salpingectomy procedure).

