6.2.2 Enrollment, Baseline, and/or Randomization

Enrollment

Patients will be considered for enrollment if they meet inclusion criteria (please refer to section 4.1). If a patient expresses a desire to undergo permanent sterilization to her provider at any time and will undergo a cesarean delivery then she is eligible for enrollment and the study coordinator will be contacted to introduce the study and obtain informed consent.

In the event the study coordinator is not available for consent (i.e., middle of the night, spontaneous onset of labor in a patient planning repeat cesarean for delivery), then an obstetrical provider listed in the IRB will be able to obtain consent for enrollment. The delivering provider will not obtain consent.

Randomization

- Initiation of study intervention relative to randomization: When patients have been enrolled in the study they will be randomized. The Dynamic Allocation System will be used for electronic randomization based on the stratification criteria. Outcome of randomization (arm) will be communicated to the surgical team prior to surgery and to the participant following surgery.
- After cesarean delivery has been performed and the surgeon feels it is safe to proceed with surgical sterilization procedure identified from randomization (salpingectomy vs BTL), the start and stop time of the surgical procedure will be recorded by the circulating RN or other obstetrical provider on a case report form. Total time of the procedure, in minutes, will be recorded.

Follow-up Visits (abstracted from the Electronic Medical Record)

- Visit 1 (24 hours post operatively)
 - Vital signs
 - Physical exam
 - Medications
 - Hemoglobin
 - Adverse events
- Visit 2: Scheduled post-partum exam 6 weeks post procedure.
 - Vital signs
 - Physical exam
 - Medications
 - Adverse events

Completion/Final Evaluation

Final visit will be at the patient's postpartum exam. Any untoward events from after the first 24 hours from the procedure to that time will be reviewed (i.e., blood transfusion, readmission to hospital, etc.). If the participant receives post-partum care at a local clinic, not Mayo Clinic Rochester, the study coordinator will call the participant to collect final evaluation data, using an IRB-approved telephone script.

Patients who decide to withdraw from the study will also be interviewed and reasons for this will be discussed and potential reasons explored.

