7.3 Adverse Events and Serious Adverse Events

Adverse Event: Is defined as any unfavorable and unintended sign (including an abnormal laboratory finding), symptom or disease temporarily associated with the use of a medical treatment or procedure that may or may not be considered related to the

medical treatment or procedure.

Adverse events are classified according to their severity.

Grade 1: Mild; asymptomatic or mild symptoms; clinical or diagnostic observations only; intervention not indicated.

- Increased pain score
- Mild anemia

Grade 2: Moderate; minimal, local or noninvasive intervention indicated

- Severe anemia not requiring transfusion

Grade 3: Severe or medically significant but not immediately life-threatening hospitalization or prolongation of hospitalization indicated; disabling limiting self-care.

- Severe anemia requiring transfusion
- Loss of one or both adnexa

Grade 4: Life threatening consequences; urgent intervention needed

- Requiring Cesarean hysterectomy
- Return to operating room

Grade 5: Death related to AE

Adverse outcomes are also problems/events that in the opinion of the principal investigator may have adversely affected the rights, safety, or welfare of the subjects or others, or substantially compromised the research data.

Given that a cesarean delivery will have also been performed prior to the tubal surgery, it will be difficult to distinguish if adverse events or serious adverse events are the direct result of the cesarean or the salpingectomies. Detailed review of the operative note will provide clarification as to which portion of the procedure is thought to have contributed to any adverse events.

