9.4.2 Secondary outcomes

1. Time in minutes in performance of BTL vs salpingectomy: Start time and stop time will be articulated by the surgeon and recorded by the circulating RN or other obstetrical provider on a case report form. Total time will be calculated
2. EBL in ml as documented in the operative report.
3. Complications as documented in the operative report and medical record
4. Pain scores as documented in patient chart

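### The participant learns her procedure after surgery, with nothing holding disclosure until pain is recorded, so blinded pain reporting is not protected

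*Combined protocol and SAP*

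**What the plan says.** **Disclosure.** Three places in the combined protocol and SAP cover it.

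- Section 3: "Post procedure, the type of sterilization procedure will be disclosed to the patient".
- Section 5.2: "after the surgery, it will be disclosed to them the procedure they had performed".
- Section 6.2.2: "Outcome of randomization (arm) will be communicated to the surgical team prior to surgery and to the participant following surgery".

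On blinding, Section 5.2 says of participants "They will be blinded to the operative intervention at the time of" enrollment and randomization. It claims nothing for the postoperative period.

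**Pain.** The secondary objectives in Section 1.2 include "length of stay, estimated blood loss (EBL) and pain scores in patients undergoing a standard BTL vs a salpingectomy". Section 9.4.2 lists, as its fourth secondary outcome, "Pain scores as documented in patient chart". Section 9.5 tests secondary endpoints with two-sided t-tests or chi-square tests at 0.05. Section 7.3 gives "Increased pain score" as an example of a Grade 1 adverse event.

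**The concern.** Pain is rated by the participant, so knowing which operation she had can influence the rating. The plan keeps the arm from her up to and through surgery, then releases it without reference to when pain is measured. If pain is charted after disclosure, a difference between arms may partly reflect expectation, and so may the absence of one. Analysis cannot restore blinding afterwards.

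Two results are exposed. One is the secondary comparison of pain scores. The other is the adverse-event count: a raised pain score is a Grade 1 event, Section 7.7 has events sought by direct questioning at each contact, and Section 8 counts Grade 1 and 2 events towards its clinical-hold threshold.

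**Working it through.** **1. The plan's own figure.** The only powered outcome is the drop in hemoglobin (Section 9.2): margin 0.5, SD 1.1, one-sided alpha 0.05, power 80%.

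n per arm = 2 × (1.645 + 0.842)² × 1.1² / 0.5² = 2 × 6.18 × 1.21 / 0.25 ≈ 59.8, rounded up to 60.

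The stated 60 per arm is reproduced. Power at 60 per arm is 0.801 by the normal formula and 0.797 by the noncentral t. The timing of disclosure changes neither figure.

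**2. Order of events.**

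- Section 3 describes, in this order: cesarean, sterilization, logging of operative time, disclosure, then the blood count at 24 to 48 hours. The order suggests disclosure before the 24-hour assessment but does not fix it.
- Sections 5.2 and 6.2.2 say only that disclosure follows surgery.
- Section 9.4.2 takes pain from the chart, with no scale, time point or assessor. Pain appears in neither the schedule (Section 6.1) nor the visit lists (Section 6.2.2).

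Disclosure has no stated time after surgery and pain has no stated time at all. No sentence requires pain to come first, so a site following the plan exactly could chart every pain score after disclosure.

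**3. What a bias would do to the pain test.** The documents give no pain scale, SD or likely shift. As an assumption, let knowledge of the arm shift the mean difference by b SDs with no true effect. With 60 per arm:

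- Standard error in SD units = √(2/60) = 0.1826.
- False-positive rate = 1 − Φ(1.960 − b/0.1826) + Φ(−1.960 − b/0.1826).

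| Assumed shift b (SD) | b / 0.1826 | False-positive rate |
|---|---|---|
| 0 | 0 | 5.0% |
| 0.1 | 0.548 | 8.5% |
| 0.2 | 1.095 | 19.5% |
| 0.3 | 1.643 | 37.6% |

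On an assumed 0–10 scale with SD 2.5, these shifts are 0.25, 0.5 and 0.75 points; the noncentral t gives 8.4%, 19.2% and 37.1%. At an assumed SD of 2.0, the same point shifts give 10.4%, 27.4% and 53.1%.

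For scale, the true pain difference detectable with 80% power is (1.960 + 0.842) × 0.1826 ≈ 0.51 SD. These figures show sensitivity to an assumed bias. They are not evidence that a bias of that size would occur.

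**The case against.** The strongest reply is that this is a design choice and breaks no promise. Blinding is claimed only for enrollment and randomization, and telling a woman promptly which permanent sterilization she received is defensible. Pain is unpowered, and it is missing from the secondary-outcome lists in the Précis objectives and Section 3. All of this stands, and it keeps the priority low. It does not remove the point, because pain is a named objective and outcome with a planned test, and participants already wait until after surgery to be told.

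The documents also do not support several stronger readings that a reader might infer.

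- *She is told straight after surgery, before any pain score.* No hour is given for either event. If disclosure came at discharge, inpatient scores would still be blinded.
- *Pain is the only self-reported outcome.* Adverse events are sought by questioning (Section 7.7), some six-week data come by telephone (Section 6.2.2), and care at outside hospitals is learned from the patient or her representative (Section 7.5).
- *Participants are led to expect more pain after salpingectomy.* The Study Risks text in Section 4.3 names bleeding, loss of an ovary and transfusion as possibly more likely with salpingectomy. Its only pain statement concerns menses after tubal ligation. No direction of bias follows.
- *Early disclosure is needless.* The plan gives no reason for its timing, but it does not show that a longer wait would be acceptable either.

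**Conclusion.** The point holds in a limited form. The plan discloses the arm after surgery, apparently before the 24-to-48-hour assessment, and nothing delays disclosure until pain is recorded. Pain, a secondary outcome tested at 0.05, can therefore be rated with knowledge of the arm.

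The size and direction of any bias are unknown. The range of roughly 8% to 53% for the false-positive rate rests wholly on an assumed scale, SD and shift. A reader might go further and conclude that the trial's main result is compromised. That does not follow: the primary outcome is a laboratory hemoglobin value, and the participant's knowledge of her arm does not affect it. This is a low-priority improvement that costs little.

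**What to change.** - **Section 9.4.2:** name the pain scale and the inpatient score to be analysed, with its time point; for example, the charted score nearest the 24-hour visit. The disclosure rule depends on this, so it must come first.
- **Sections 3, 5.2 and 6.2.2:** disclose the procedure after that score is charted and before discharge, with earlier disclosure on request or if a complication requires it. Disclosure need not wait for the blood count.
- **Case report form:** record the time of disclosure.
- **Section 9.5:** report pain and adverse events collected after disclosure, including all six-week data, as unblinded.

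The cost is protocol and consent wording, one extra data field, and an instruction to ward staff not to volunteer the arm. With a 24-hour pain score, the participant waits about a day. Sample size and power are unchanged. The surgical team still knows the arm, and six-week reports remain unblinded.
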